8.1.2. Sensitivity Analyses

Randomized subjects who withdraw consent to participate in the study will not be replaced. The early termination rate is estimated to be 10%. To the extent possible, attempts will be made to minimize the amount of missing data through measures planned in the study conduct, but if data are missing for the primary endpoints, the number, timing, pattern, and reason for the missing value will be summarized. The reason for missing value will be evaluated to investigate possible implications of missing values in efficacy assessments. The dropout patterns will be assessed by Kaplan-Meier plots, if applicable, to assess whether they differ between treatment groups. If there are missing values for the primary analysis, only available data will be analyzed and data obtained after rescue will not be excluded. To account for subjects for whom the post-baseline endpoint (ie, at the time when the last post-baseline double-blind assessment was performed) occurs at a time point before Week 24, a MMRM approach will be used as the primary method. It is assumed that the majority of the missing values will be one of the following:

- "Missing Completely at Random" (ie, probability of an observation being missing does not depend on observed or unobserved measurements) or
- "Missing at Random" (ie, probability of an observation being missing depends only on observed measurements)

In such situations, likelihood-base methods like MMRM are appropriate.

Sensitivity analyses will be performed as:

- 1. A multiple imputation method will be used to impute missing observations (including observations obtained after rescue medication) in the ITT Analysis Set prior to carrying out the MMRM analysis. All intermediate missing, drop-out, and data after rescue medication will be imputed.
- 2. A multiple imputation method will be used to impute missing observations (not including observations obtained after rescue medication) in the ITT Analysis Set prior to carrying out the MMRM analysis. All intermediate missing and drop-out will be imputed.

1007728

Observed data after rescue medication will be used in the MMRM analysis and not considered missing.

3. A last observation carried forward (LOCF) method will be used to impute the missing observations in the ITT Analysis Set. Subjects who are rescued before Week 24 will have their HbA1c recorded at the time of rescue and carried forward.

For sensitivity analysis 1 and 2, data will be imputed in the framework of a pattern mixture model (PMM) with placebo-based pattern imputation for missing visits. The method described here is based on methodology described by Little and Yau (1996) and extended in a PharmaSUG paper by Ratitch and O'Kelly (2011). The concept for the imputation used here is that subjects who drop out of the study from the active treated arms will exhibit the same evolution of the disease under study as those subjects assigned to the placebo arm. It is assumed, as well, that subjects who discontinue from the placebo arm would have the same evolution of the disease as those subjects on the placebo arm who remained in the study. The three-step approach outlined below will be followed (Ratitch B and O'Kelly M, 2011):

- 1. Non-monotone (intermediate visits) missing data will be imputed first using the Monte Carlo Markov Chain method under the Missing at Random (MAR) assumption in all treatment arms (using the MCMC statement in PROC MI). Multiple chains option (CHAIN=MULTIPLE option in the MCMC statement of PROC MI) will be used. For the non-monotone imputation of the HbA1c missing data, a multivariate normal model will be used including variables for the HbA1c at baseline and all post-baseline visits within each treatment group.
- After the non-monotone missing data have been imputed, the remaining monotone missing data will be imputed under the Missing Not at Random (MNAR) assumption that subjects who withdraw from the bexagliflozin group will have correlations with future (post-withdrawal) visits similar to subjects in the placebo group, adjusted for baseline covariates and observed outcomes prior to withdrawal. Monotone missing data of withdrawn subjects from the placebo group will be imputed under the MAR assumption and will follow the pattern of placebo completers. In other words, monotone missing values of the HbA1c will be imputed for all subjects who withdrew from the study (regardless of treatment group) using an imputation model at each time point estimated from subjects with available data in the placebo group only. A regression imputation model for the HbA1c at each time point t will include explanatory variables including background anti-diabetes treatment status (treatment naïve or not) and HbA1c at all previous time points, including baseline. Data from bexagliflozin group with time t data observed will not be used to impute time point t. Imputations will be performed using a sequence of regression-based imputations (using PROC MI statement MONOTONE REG) for each post-baseline time point as described in (Ratitch B and O'Kelly M, 2011).

1007728

3. Imputed data in each of the multiple imputed datasets will be analyzed using the same mixed model for repeated measures as in the primary analysis. The results from all imputed datasets will be combined using the Rubin's combination rule (PROC MIANALYZE).

The sample SAS codes can be found in Appendix 1.

The number of imputation will be determined using the method described by White, et.al., 2011. We will use Bodner's approximation to estimate the fraction of missing information (FMI) as the proportion of the incomplete cases in the data. Since the parameter of interest is the mean changes from baseline in HbA1c at Week 24 for bexagliflozin and placebo groups, FMI will be approximated using the proportion of subjects missing Week 24 values. As indicated by Bodner, this is a very conservative approach and will work with FMI≤0.5. The number of imputations m will be determined to provide sufficient level of reproducibility using formula: m≥100×FMI

as recommended by White. The Monte Carlo error of the P-value using m imputation datasets will be approximately 0.01 when the true P-value is 0.05, and 0.02 when the true P-value is 0.1.

At least 10 datasets will be imputed. We will examine the FMI estimated from the combined results. If it is much larger than our initial approximation, a considerable volatility is observed from the imputed datasets. In this case, we will increase the number of m using the estimated FMI.

For sensitivity analysis using LOCF, the observed data and the imputed values will be analyzed using the same MMRM model. Model will include terms for background anti-diabetes treatment status (treatment naïve or not), treatment, and the baseline HbA1c value as a fixed effect covariate. LS mean treatment differences between the bexagliflozin group and the placebo group will be estimated from the model with the corresponding p-values and their two-sided 95 % CIs presented.

8.1.3. Subgroups

The primary efficacy endpoint will be summarized and analyzed by the following subgroups:

- Age (<65 years or ≥65 years)
- Gender (male or female)
- Race (white or caucasian; black or African-American; other)
- Baseline HbA1c (7.0% to 8.5% or 8.6% to 10.5%)
- Background anti-diabetic treatment status (treatment-naïve or on treatment)

1007728

• Country (USA or Canada)

8.2. SECONDARY EFFICACY ENDPOINT(S) AND ANALYSES

The key secondary efficacy endpoints include:

- Change in SBP from baseline to week 24.
- Change in body weight from baseline to week 24 in subject with BMI≥ 25 kg/m²

The exploratory efficacy endpoints include:

- Change from baseline in HbA1c over time
- Proportion of subjects with HbA1c of < 7% over time
- Change from baseline FPG over time.

8.2.1. Key secondary efficacy endpoints and analyses

A hierarchical testing procedure will be applied to these endpoints in the sequence provided above. These key secondary endpoints will only be tested sequentially when significant treatment differences are established for the primary efficacy endpoint in the comparisons between the bexagliflozin and placebo groups.

Analysis for key secondary endpoints will be based on the ITT analysis set and repeated for the PP analysis set. The sensitivity analyses stated in Section 8.1.2 will be performed on all key secondary endpoints.

8.2.1.1. Change in SBP from baseline to week 24

This will be tested if the primary efficacy endpoint is significant. Change from baseline in sitting SBP at week 24 will be analyzed using the MMRM ANCOVA model with unstructured covariance assumption. The model will include terms for treatment, visit, treatment-by-visit interaction, baseline HbA1c and background anti diabetes treatment status as fixed effects and the corresponding baseline SBP value as an additional fixed effect covariate. Treatment comparison p-values and difference at week 24 will be estimated from the model, with the two-sided 95% CIs of the treatment difference also presented. If the model does not converge with the unstructured correlation assumption, an autoregressive (1) model will be used.

1007728

8.2.1.2. Change in body weight from baseline to week 24 in subjects with a BMI ≥ 25 kg/m²

This will be tested if the primary efficacy endpoint and the key secondary endpoint-change from baseline SBP are significantly different between bexagliflozin and placebo groups based on ITT analysis set. The comparison of change in body weight between randomized treatments at week 24 will be carried out using the ANCOVA model. The model will include terms for treatment, background anti diabetes treatment status and baseline HbA1c as fixed effects, and the corresponding baseline weight value as an additional fixed effect covariate. Treatment comparison p-values and difference at week 24 will be estimated from the model, with the two-sided 95 % CIs of the treatment difference also presented. If the primary hypothesis is not significant, the nominal p-value will not be used for inferential purposes.

8.2.2. Exploratory secondary efficacy endpoints and analyses

All endpoints in this section are exploratory. No sensitivity analyses and adjustment for multiple comparisons will be conducted. Nominal p-values will be used to examine any trends in these endpoints.

8.2.2.1. Changes from baseline in HbA1c, and in FPG over time

These endpoints will be analyzed using similar MMRM ANCOVA models as for the key secondary efficacy endpoint, Section Error! Reference source not found. The treatment-by-visit interaction term will be removed if it is not significant. Of interest in the MMRM ANCOVA model is the difference between treatments on these endpoints across all post-baseline time points. Also, changes from baseline for each endpoint will be estimated and analyzed at each study visit using this MMRM model. Specifically, for each endpoint, treatment difference in least squares means will be estimated by visit from the model with the corresponding p-values and the two-sided 95% CIs of the difference between treatments.

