9.6.2 Exploratory Efficacy Endpoints

The exploratory secondary efficacy endpoints include:

- Change from baseline in HbA1c over time
- Proportion of subjects reaching HbA1c < 7% over time
- Change from baseline in FPG over time

For changes from baseline in HbA1c, FPG over time, a similar MMRM ANCOVA model will be used as for the key secondary efficacy endpoint of change in SBP at week 24 in subjects with baseline SBP \geq 130 mmHg (the treatment-by-visit interaction term will be removed if not significant). Of interest in the MMRM ANCOVA model is the difference between treatments on these endpoints across all post-baseline time points. Also, changes from baseline for each endpoint will be estimated and analyzed at each study visit using this MMRM model. Specifically, for each endpoint, treatment difference in least squares means will be estimated by visit from the model with the corresponding p-values and the two-sided 95% CIs of the difference between treatments.

Endpoints measuring proportions over time will be analyzed using generalized estimating equation logistic regression using similar independent variables as the MMRM ANCOVA models above (the treatment-by-visit interaction term will be removed if not significant), and using an unstructured correlation structure (or autoregressive(1) if the model with the

unstructured structure does not converge). Of interest is the difference between treatments across all post-baseline time points. Also, odds ratios will be estimated from the model with the corresponding p-values and their two-sided 95% CIs presented at each visit.

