This hypothesis will be tested based on ITT analysis set using all observed data and a mixed model repeated measures (MMRM) approach. The MMRM model will include terms for background anti-diabetes treatment status (treatment naïve or not), treatment, visit, treatment-by-visit interaction and the baseline HbA1c value as a fixed effect covariate. Country will be used as a fixed effect if pooling by country is used. The analysis will evaluate the mean change from baseline in HbA1c over the 24-week double-blind treatment period. An unstructured covariance will be used to model the within-subject correlation. The Kenward-Roger approximation will be used to estimate denominator degrees of freedom. If the model with the unstructured covariance structure does not converge, an autoregressive(1) covariance structure will be used. HbA1c values obtained after the start of rescue medication will not be excluded from the analysis.

Based on the MMRM model, the treatment and treatment-by-visit interaction terms allow for comparisons of the treatment groups at each visit, and over week 6 to week 24. Least squares (LS) mean treatment differences between the bexagliflozin group and the placebo group at week 24 will be estimated from the model with the corresponding p-values and their two-sided 95 % CIs presented. Sample SAS code will be provided in Appendix 1.

Descriptive statistics (n, mean, Q1, median, Q3, SD, minimum, and maximum) will be reported by treatment group and visit, along with the least squares means, differences

1007728

between LS means, a 2-sided 95% confidence interval for each difference, p-values from the model effects. In addition, the LS means with standard errors of the change from baseline over time and difference between treatment groups with 95% will be presented graphically for the ITT population.

For supportive analyses, the primary efficacy endpoint will be analyzed with observed available data using the PP analysis set in a similar manner as above.

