8.2.2.2. Proportions of subjects with HbA1c of < 7% over time

This endpoint will be analyzed using generalized estimating equation logistic regression. The treatment-by-visit interaction term will be removed if not significant. An unstructured correlation structure will be used (or autoregressive(1) if the model with the unstructured structure does not converge). Of interest is the difference between treatments across all post-baseline time points. Also, odds ratios will be estimated from the model with the corresponding p-values and their two-sided 95% CIs presented at each visit. The odds ratios of bexagliflozin group over the placebo group at each visit and across all post-baseline time points will be estimated from LS means based on the model with the corresponding p-values and their two-sided 95 % CIs presented. Sample SAS code will be provided in Appendix 1.

1007728

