17. INDEX OF FIGURES

Number	Title
Figure 14.1.1	Kaplan-Meier Plot of Time to Discontinuation by Week 26 (ITT Analysis Set)
Figure 14.2.1.1	LS Mean (± SE) Change from Baseline in HbA1c (%) (ITT Analysis Set)
Figure 14.2.1.2	LS Mean Difference (95% CI) in Change from Baseline in HbA1c (%) (ITT Analysis Set)
Figure 14.2.1.3	LS Mean (± SE) Change from Baseline in HbA1c (%) (PP Analysis Set)
Figure 14.2.1.4	LS Mean Difference (95% CI) in Change from Baseline in HbA1c (%) (PP Analysis Set)
Figure 14.2.1.5	Sensitivity Analysis 1: Multiple Imputation LS Mean Difference (95% CI) in Change from Baseline in HbA1c (%) Including Observations Obtained After Rescue Medication (ITT Analysis Set)
Figure 14.2.1.6	Sensitivity Analysis 2: Multiple Imputation LS Mean Difference (95% CI) in Change from Baseline in HbA1c (%) Excluding Observations Obtained After Rescue Medication (ITT Analysis Set)
Figure 14.2.2	LS Mean (± SE) Change from Baseline in Fasting Plasma Glucose (mmol/L) (ITT Analysis Set)
Figure 14.2.3	Proportion of Subjects Reaching HbA1c < 7% (ITT Analysis Set)

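### Deleting a non-significant treatment-by-visit term makes the by-visit effects for FPG and for HbA1c <7% identical at all four visits

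*SAP*

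**What the plan says.** SAP 8.2.2.1 covers change in HbA1c and FPG over time. It specifies an MMRM modelled on the one for systolic blood pressure and adds: "The treatment-by-visit interaction term will be removed if it is not significant". It also requires that "treatment difference in least squares means will be estimated by visit from the model with the corresponding p-values and the two-sided 95% CIs" be reported.

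SAP 8.2.2.2 covers the GEE logistic model for HbA1c <7%: "The treatment-by-visit interaction term will be removed if not significant". It asks for "The odds ratios of bexagliflozin group over the placebo group at each visit and across all post-baseline time points" from that model. Protocol 9.6.2 has the same deletion rule for both model types and says: "Also, changes from baseline for each endpoint will be estimated and analyzed at each study visit using this MMRM model".

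Neither document says that the by-visit results come from the model before deletion. No separate significance level is given for the interaction test, so the 0.05 default in SAP 6.1 is taken to apply.

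The primary HbA1c model in SAP 8.1.1 has no deletion rule. It relies on the term being present: "the treatment and treatment-by-visit interaction terms allow for comparisons of the treatment groups at each visit, and over week 6 to week 24".

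**The concern.** A by-visit treatment difference needs a model in which the difference can vary by visit. The rule removes that freedom whenever the interaction test fails to reject, and the plan then asks the reduced model for by-visit results. The reader would see one effect, interval and p-value printed four times. A failed 3-df test, in a trial sized for something else, could be taken as evidence that the effect is constant.

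For FPG and HbA1c <7% this is the only planned model-based time course. If the FPG least-squares-mean figure (Figure 14.2.2) is drawn from this model, its two curves will be parallel by construction. SAP 8.2.2 gives the purpose of these analyses: "Nominal p-values will be used to examine any trends in these endpoints". A model forced to show a constant effect cannot show a trend in effect.

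For HbA1c change the problem is different. The primary MMRM already gives a valid time course, so the rule risks a second, conflicting set of by-visit differences in Table 14.2.1.5.

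**Working it through.** **The plan's sample size.** SAP 3.6 assumes a difference of 0.5, SD 1.0, and 128 and 64 evaluable subjects. The noncentrality is 0.5 / √(1/128 + 1/64) = 0.5 / 0.1531 = 3.27; with 190 df the two-sided 5% t-test has 90.1% power, which agrees with the stated 90%. The trial is therefore sized for one week-24 difference, not for a 3-df test of whether four differences are equal.

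**Algebra.** With the interaction, the treatment contrast at visit v is β + γ_v. Without it, the contrast is β at every visit, because the visit and covariate terms cancel between arms. In the GEE the same holds for the log odds ratio.

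**Illustration.** Both models were fitted to one simulated data set (128/64, four visits).

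| Model | Week 6 | Week 12 | Week 18 | Week 24 |
|---|---|---|---|---|
| MMRM difference, term kept (interaction p = 0.82) | -0.488 | -0.485 | -0.566 | -0.496 |
| MMRM difference, term deleted (SE 0.116) | -0.499 | -0.499 | -0.499 | -0.499 |
| GEE odds ratio, term kept (interaction p = 0.74) | 1.84 | 1.60 | 1.62 | 2.49 |
| GEE odds ratio, term deleted | 1.878 | 1.878 | 1.878 | 1.878 |

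In the reduced GEE only the odds ratio is forced to be constant. Model-based risk differences still vary (0.075, 0.077, 0.100, 0.111).

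**Size by hand for one case.** Assume effects of -0.30/-0.45/-0.50/-0.50 SD, 140/70 subjects, and correlation 0.6 between all visits.
- The reduced model estimates the average, -1.75/4 = -0.4375.
- Its SE is √[(1/140 + 1/70) × (1 + 3 × 0.6)/4] = √(0.02143 × 0.70) = 0.122.
- At week 6 the error is 0.1375, or 1.12 SE, so coverage is Φ(0.84) - Φ(-3.08) = about 80%.
- At week 24 the error is 0.0625, or 0.51 SE, so coverage is Φ(1.45) - Φ(-2.47) = about 92%.

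**Simulation of the whole rule.** 6000 trials per scenario, 140/70, complete data, no covariates, compound symmetry or AR(1), correlation 0.6 and 0.8, interaction tested at 0.05. All time profiles and placebo rates are assumptions. Coverage is over all trials unless stated.
- Rising effect (as above): term dropped in 47-83% of trials. Among those trials, coverage is 79-87% at week 6 and 88-93% at week 24. Over all trials it is 82-89% and 88-94%, with mean bias of 0.05-0.08 SD and 0.02-0.05 SD.
- Fading effect (-0.50/-0.50/-0.45/-0.30): the shortfall moves to week 24, with coverage of 82-89%.
- Milder rise (-0.40, then -0.50): about 90-92% at week 6.
- Constant effect: 94-95%, no bias.
- HbA1c <7%, placebo rate 15-20%, odds ratios 1.5/2.2/2.6/2.6: dropped in 69-77%; coverage 70-76% at week 6 and 91-93% at week 24.
- HbA1c <7%, odds ratios 2.0/2.5/2.6/2.6: 89-91% at week 6. Constant 2.5: 95%.
- Term always kept: about 95% in every scenario.

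The binary runs used by-visit log odds ratios with a robust covariance as a large-sample stand-in for the GEE. Repeating the continuous rising case with 128/64 gave 51-85% dropped and 83-89% coverage at week 6.

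**FPG in its own units.** Assume effects growing from -0.9 to -1.5 mmol/L, SD 2.0-2.5, AR(1) correlation 0.5-0.7, and 128/64 subjects. The term is then dropped in 72-85% of 400 simulated trials per setting, and the reduced model reports about -1.2 at every visit.

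**The case against.** The strongest reply is about weight. These endpoints are exploratory with nominal p-values, and no decision in the plan depends on the by-visit values. The documents name the across-visit effect as the quantity of interest and add the by-visit results as a further output. That across-visit effect is little affected by deletion: in the rising case the reduced model targets -0.4375 under compound symmetry, which is the plain average, and about -0.42 under AR(1) with correlation 0.6. SAP 8 also requires descriptive summaries by treatment and visit whatever the model, so a real trend would remain visible. All of this stands and limits the severity.

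A second reply is that the size rests on assumed profiles. That is true. The documents give no time course for FPG, and a constant effect produces no bias. The shortfall is mainly at the ends of the schedule; in the rising case week 12 coverage stays at 94-95%. For HbA1c, however, Protocol 3.3.1 says the measure reflects control over 2 to 3 months, so an effect still developing at week 6 is plausible, and HbA1c <7% inherits that.

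A third reply is that the by-visit results may have been meant to come from the model before deletion. The Appendix 1 code is not in the supplied text, so this cannot be excluded, but the written text points to the reduced model and should say otherwise if that was intended.

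**Conclusion.** The concern holds. That the results are identical at all four visits after deletion is algebra and needs no assumption beyond a non-significant interaction test. Each endpoint is affected only if its own test is non-significant. How wrong the by-visit results would be depends on assumed profiles: no bias if the effect is constant; whole-procedure coverage of about 82-89% at the worst visit for the steeper HbA1c-scale profiles; and 70-76% at week 6 for the steeper odds-ratio profile. The primary HbA1c test, the key secondary tests and the type I error rate are untouched. This should be corrected, but it does not threaten the trial's main conclusions.

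**What to change.** In SAP 8.2.2.1 and 8.2.2.2, replace the removal rule with: *The treatment-by-visit interaction term will be retained regardless of its significance.* Then:
- Take all by-visit effects from that model.
- Define the across-visit effect as the equally weighted contrast of the four visit differences (log odds ratios in the GEE).
- State that by-visit HbA1c differences are those of the primary MMRM in SAP 8.1.1, so that only one set is reported.

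Protocol 9.6.2 should carry the same wording. If an amendment, which needs IRB/IEC approval under Protocol 10.2, is not wanted for this alone, the SAP change is enough, because Protocol 9.1 makes the SAP the final plan. SAP 12, which now declares no departure from the protocol, must then record it.

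No new data are needed. If the effect is truly constant, the cost is wider by-visit intervals. The by-visit SE is √(1/140 + 1/70) = 0.146 SD, against 0.111-0.135 for the common effect over the correlations considered. The smallest common-effect SE is √(0.02143 × 1.6/2.8) = 0.111 (AR(1), 0.6) and the largest is √(0.02143 × 3.4/4) = 0.135 (compound symmetry, 0.8), so by-visit intervals are about 8-32% wider. The equally weighted contrast loses almost nothing. Under compound symmetry its SE equals the common-effect SE. Under AR(1) with correlation 0.6 it is √(0.02143 × 9.472/16) = 0.113, about 2% wider than 0.111.
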